### 5.3.1.4 *Progression to Intubation or Death within 35 days of First Dose or Randomisation*

Intubation is defined by the OSCi as a score between 6 and 7. Death is defined by an OSCi score of 8. Any patient with an OSCi score at any post baseline assessment up to and including Day 35 of 6 or more will be considered as progressed to intubation or death.

## Statistical Analysis Plan (RotW)

Final v1.0, 08FEB2022

SG018

All patients should have an OSCi score of 4 at baseline, however in the event a patient is enrolled with an OSCi score of  $\geq 6$  at baseline this patient will be excluded from all analyses of progression to intubation or death.

Day 35 will be determined by the study schedule, which may be more than 35 days after randomisation if randomisation occurs before Day 1.

#### 5.3.1.5 *Death within 35 days of First Dose or Randomisation*

Deaths will be identified by an OSCi score of 8 at any post baseline assessment up to and including Day 35, a fatal Adverse Event (AE) on or before Day 35 or withdrawal due to a fatal AE on or before Day 35.

Patients who die after Day 35 will be considered alive for the derivation of death within 35 days of first dose or randomisation.

Day 35 will be determined by the study schedule, which may be more than 35 days after randomisation if randomisation occurs before Day 1.

#### 5.3.2 *Derivation of NEWS2 Scores*

The NEWS2 score will be calculated using the following six parameters:

1. respiration rate
2. oxygen saturation
3. systolic blood pressure
4. pulse rate
5. level of consciousness or new confusion
6. temperature.

Each parameter will be assigned a score between 0 and 3 according to the chart in [Appendix I](#) and the NEWS2 score is calculated as the sum of the individual parameter scores, providing that all respective scores are non-missing. If any individual parameter scores are missing the NEWS2 score will also be missing.

For the pre-treatment/pre-baseline assessment, the NEWS2 score will be derived using data from scheduled vital signs page of the eCRF. For any post-baseline assessments, the NEWS2 score will be derived using data from the scheduled NEWS2 page.

NEWS2 score will also be categorised as per table 1.

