6.8 Vital Signs

Vital signs include temperature, respiratory rate, heart rate and blood pressure should be recorded daily whilst the patient is hospitalised. Vital signs should be assessed at the same time as the daily physical examination. When the patient is discharged home vital sign assessments will not be recorded.

Blood pressure and pulse should be measured in the supine position and it is recommended that the patient should have rested quietly for at least 3 minutes prior to the measurement.

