6.9 NEWS2

The data required for NEWS2 will be collected by the site staff and NEWS2 will be calculated by the Sponsor.

NEWS2 is a tool developed by the Royal College of Physicians, which improves the detection and response to clinical deterioration in adult patients and is a key element of patient safety and improving patient outcomes (12).

NEWS2 is based on a simple aggregate scoring system in which a score is allocated to physiological measurements, already recorded in routine practice, when patients present to, or are being monitored in hospital.

Six simple physiological parameters form the basis of the scoring system:

1. Respiration rate
2. Oxygen saturation
3. Any supplementary oxygen
4. Temperature
5. Systolic blood pressure
6. Heart rate
7. Alert, Voice, Pain, Unresponsive.

The highest NEWS2 score for each calendar day should be collected. The highest NEWS2 score will be recorded daily, for each calendar day, whilst the patient is hospitalised. When the patient is discharged home, NEWS2 will not be recorded.

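### SAP 5.3.2 leaves supplementary oxygen out of the NEWS2 sum, although Protocol 6.9 lists it, and declares no change

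*SAP*

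**What the plan says.** Protocol 2.4 and SAP 4.2.3 make change in NEWS2 while in hospital a secondary endpoint.

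Protocol 6.9 opens its list with "Six simple physiological parameters form the basis of the scoring system" but then numbers seven items. Item 2 is oxygen saturation and item 3, separately, is "Any supplementary oxygen". On who derives the score it says: "The data required for NEWS2 will be collected by the site staff and NEWS2 will be calculated by the Sponsor". It adds that "The highest NEWS2 score for each calendar day should be collected" and that "When the patient is discharged home, NEWS2 will not be recorded".

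SAP 5.3.2 states: "The NEWS2 score will be calculated using the following six parameters". It names respiration rate, oxygen saturation, systolic blood pressure, pulse rate, consciousness or new confusion, and temperature. Each is scored 0 to 3 from the Appendix I chart, and "the NEWS2 score is calculated as the sum of the individual parameter scores". If any one of them is missing, the total is missing. Baseline values come from the vital signs page (SAP 9.3.3 adds the level-of-confusion form), and later values come from the NEWS2 page.

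SAP 9.3.3 plans descriptive summaries of the absolute score and of change from baseline. SAP section 15, which lists departures from the protocol, covers the rebound period, the covariates and the per-protocol estimands, but not NEWS2.

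**The concern.** The Sponsor calculates the score, so the SAP rule decides what is reported. Followed as written, that rule leaves out an item the protocol lists, and nothing shows that this was intended.

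The item matters in this trial because inclusion criterion 4 requires oxygen by prongs or mask (OSCI 4). If oxygen use carries points, the six-item total understates severity at entry for every eligible patient. It also gives no credit when a patient comes off oxygen while still in hospital. The reported result would carry the name NEWS2 without being the score the protocol describes.

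**Working it through.** **Comparing the two lists**

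| Protocol 6.9 | SAP 5.3.2 |
|---|---|
| Respiration rate | Respiration rate |
| Oxygen saturation | Oxygen saturation |
| Any supplementary oxygen | not listed |
| Temperature | Temperature |
| Systolic blood pressure | Systolic blood pressure |
| Heart rate | Pulse rate |
| Alert, voice, pain, unresponsive | Consciousness or new confusion |

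The SAP's own count of six is reproduced. The protocol has seven items, and the only one with no counterpart is supplementary oxygen. The consciousness items are worded differently but cover the same domain.

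**Effect on the score**

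Inputs:
- w is the number of points for being on oxygen. Appendix I is redacted, so w cannot be read. I assume w = 1, 2 or 3, the non-zero part of the SAP's per-item range.
- All eligible patients are taken to be on oxygen at baseline (inclusion criterion 4).
- p is the share of an arm's in-hospital patients on a given day whose highest score was taken off oxygen. The documents give no value, so the values used are assumptions.

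For one patient at one assessment:

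full score = six-item score + w × (1 if on oxygen, 0 if off)

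With baseline on oxygen:

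full change = six-item change − w × (1 if off oxygen at the day's highest score, otherwise 0)

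The change is therefore correct while the patient is scored on oxygen, and improvement is understated by w when scored off oxygen. After discharge there is no error, because NEWS2 is no longer recorded. For example, a six-item score falling from 5 to 2 is a change of −3 under the SAP. With oxygen counted at baseline only, it is 2 − (5 + w), which is −4, −5 or −6 for w = 1, 2 or 3.

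Understatement of an arm's mean improvement, w × p:

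| p | w = 1 | w = 2 | w = 3 |
|---|---|---|---|
| 10% | 0.1 | 0.2 | 0.3 |
| 30% | 0.3 | 0.6 | 0.9 |
| 50% | 0.5 | 1.0 | 1.5 |

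Error in the between-arm difference, w × (p in SNG001 − p in placebo):

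| Difference in p | w = 1 | w = 2 | w = 3 |
|---|---|---|---|
| 0 | 0 | 0 | 0 |
| 5 percentage points | 0.05 | 0.10 | 0.15 |
| 10 percentage points | 0.10 | 0.20 | 0.30 |
| 20 percentage points | 0.20 | 0.40 | 0.60 |

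**Risk categories**

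SAP Table 1 cuts the total at 5 and at 7. On totals alone, adding w for a patient on oxygen changes the category at six-item scores of 4 and 6 if w = 1, and at 3 to 6 if w = 2. If w = 3 it changes at 0 to 6, partly because a single item scored 3 triggers the low-medium category. The readable text derives these categories but plans no summary of them, so I give this no weight in the conclusion.

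**The case against.** Four points can be made against the concern.

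1. **The protocol contradicts itself first.** Its lead-in says six, and the SAP's six agrees with that count. This stands as a likely source of the error. It does not justify dropping a numbered item without comment, and it means that both documents need correcting.

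2. **The chart is redacted.** It may have an oxygen row, or may score saturation differently on oxygen and on air. This stands as a limit on the size of the effect, which can only be stated conditionally. It does not remove the mismatch, because 5.3.2 restricts the sum to the six parameters it names. An oxygen row would conflict with that text, and a chart without one would leave an undeclared departure from Protocol 6.9.

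3. **The magnitudes rest on assumed w and p.** This also stands. Moreover, the protocol asks for each day's highest score. If oxygen adds points and the highest is chosen on the full score, days spent partly on oxygen will tend to be represented by an on-oxygen reading. That lowers p and so lowers the error in change from baseline. No between-arm distortion has been shown; there is none if p is equal in the two arms.

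4. **The consequences are small.** NEWS2 has no model, no test and no place in the multiplicity scheme. Weaning is visible in OSCI (4 to 3) and in the oxygen-use table of SAP 10.2. All of this is true and limits the severity, but neither source corrects a score reported as NEWS2.

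**Conclusion.** The concern holds. The omission and the absence of a declared change are plain from the text, and I hold them with high confidence. The effect on the score depends on oxygen carrying points. If it does, baseline is w too low for every eligible patient. With w of 1 to 3 and p of 10% to 50%, an arm's mean improvement on a given day is understated by 0.1 to 1.5 points. The between-arm error runs from zero to 0.6 points for differences in p of up to 20 percentage points. Both w and p are assumptions.

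The impact is confined to a descriptive secondary endpoint and leaves the primary and key secondary endpoints, power and alpha unchanged. It should be corrected, but it does not threaten the trial's main conclusions.

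**What to change.** Add supplementary oxygen (yes/no) to the parameter list and the sum in SAP 5.3.2, scored from the Appendix I chart. Reconcile the count and list in Protocol 6.9 with SAP 5.3.2 and Appendix I.

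State the data source. At baseline, use the vital signs page, which already holds oxygen flow (SAP 5.3.9). After baseline, use the same NEWS2 assessment that gives the day's highest score. Vital signs follow a different clock, since "Vital signs should be assessed at the same time as the daily physical examination". Oxygen status recorded at another time of day should therefore not be substituted without a flag.

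If the NEWS2 page does not record oxygen use, or the omission is intended, declare it in SAP section 15 and label the result a modified NEWS2 without the oxygen item.

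The cost is SAP wording and one derived variable. No new data are needed if the NEWS2 page holds oxygen use, which must be confirmed first because its fields are not shown. The drawback is that a seventh item may create more missing totals under the any-missing rule. If each item is missing independently with probability m (assumed), the share of complete scores moves from (1 − m)^6 to (1 − m)^7:

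| m | Six items | Seven items |
|---|---|---|
| 1% | 94.1% | 93.2% |
| 2% | 88.6% | 86.8% |
| 5% | 73.5% | 69.8% |

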**Table 1: NEWS2 Clinical Risk Categories**

Criteria	Clinical Risk Category
NEWS2 score between 0 and 4	Low
Score of any individual parameter of 3	Low-medium
NEWS2 score of 5 or 6	Medium

## Statistical Analysis Plan (RotW)

Final v1.0, 08FEB2022

SG018

NEWS2 score of 7 or more	High
--------------------------	------

If a patient meets the criteria for more than one category the worst category will be selected.

### 5.3.3 Derivation of Duration of Symptoms at Baseline

Duration of symptoms at baseline, which will be considered for subgrouping, will be calculated as date of randomisation – date of initial COVID-19 symptoms + 1.

### 5.3.4 Derivation of EQ-5D-5L Index Values

Index values will be calculated for patients in the home setting from their EQ-5D-5L profiles using the method proposed by van Hout B, Janssen MF et al [2], as described below.

The EQ-5D-5L profile for an individual is found by combining the scores from each of the five dimensions to form a five-digit number in the following order: mobility, self-care, usual activities, pain/discomfort and anxiety/depression. Each dimension is graded with a score between 1 and 5 where 1 indicates no problems and 5 indicates unable to/extreme problems. Therefore, a patient with no problems in any of the five dimensions will have a profile 11111 and a patient with no problems with mobility, slight problems with washing or dressing, moderate problems with doing usual activities, severe pain or discomfort and extreme anxiety or depression will have a profile of 12345.

Each profile score is used to calculate an index value for the country of residence. Index values can be a maximum of 1 and a higher index value indicates a better quality of life, e.g. someone with a profile of 11111, indicating no problems would have an index value of 1.000.

The crosswalk value sets found on the EuroQol website: <https://euroqol.org/eq-5d-instruments/eq-5d-5l-about/valuation-standard-value-sets/crosswalk-index-value-calculator/>.

Because this international study includes a number of countries where a crosswalk index is not available the UK crosswalk index will be used for all patients. To help interpret quality of life internationally the Level Sum Score (LSS) will also be calculated as proposed in Feng et al 2021 [10]. The LSS is calculated by assigning a numerical value to each response level (i.e., 1 for “no problems”, 5 for “extreme problems”/“unable to”) and summing these values across the five items, resulting in a score from 5 (11111, no problems on any dimension) to 25 (55555, extreme problems on all dimensions) for the EQ-5D-5L.

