- b. Progression to intubation or death, defined by the WHO OSCi score of 6 or above within 35 days of first dose (or randomisation date if the patient is not dosed).
- c. Death within 35 days of first dose (or randomisation date if the patient is not dosed).

Secondary Endpoints:

- a. Recovery, where recovery is defined as the WHO OSCi score of 1 or below, with no rebound at subsequent assessments, at Days 7, 14, 21 and 28.
- b. Hospital discharge by Days 7, 14, 21 and 28.
- c. Improvement across the entire WHO OSCi by Days 7, 14, 21 and 28.
- d. Changes in breathlessness, cough and sputum scale (BCSS) score during the study

period, including disaggregated breathlessness and cough scores.

- e. Changes in National Early Warning Score 2 (NEWS2) during the hospitalisation period.
- f. Daily assessment of COVID-19 symptoms and limitation of usual activities.
- g. Quality of life measured using EQ-5D-5L.
- h. Long-COVID-19 symptoms.
- i. Safety and tolerability – vital signs, AEs, concomitant medications, and immunogenicity.

Exploratory Endpoint:

CCI	CCI
	CCJ
CCI	

Inclusion criteria:

To be eligible for randomisation into this study, each patient must fulfil the following criteria:

1. Male or female, ≥ 18 years of age at the time of consent.
2. Admitted to hospital due to the severity of their COVID-19.¹
3. Positive virus test for SARS-CoV-2 using a validated molecular assay or antigen assay. Patients who had a positive virus test for SARS-CoV-2 prior to hospitalisation will be randomised no later than 48 hours after hospital admission. If the virus test is performed more than 96 hours prior to hospitalisation, the test will have to be repeated in the hospital prior to randomisation. Only patients whose repeated virus test is positive will be randomised, no later than 48 hours after confirmation of SARS-CoV-2 infection.
- Patients who had their first positive virus test for SARS-CoV-2 after hospitalisation will be randomised no later than 48 hours after confirmation of SARS-CoV-2 infection.
4. Require oxygen therapy via nasal prongs or mask (WHO OSCI score of 4).
5. Provided informed consent.
6. Female patients must be ≥ 1 year post-menopausal, surgically sterile, or using a highly effective method of contraception. Acceptable highly effective methods of contraception include;
 - bilateral tubal occlusion
 - intrauterine device (provided coils are copper-banded)
 - levonorgestrel intrauterine system (e.g., MirenaTM)

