3.1 Criteria for Inclusion and Exclusion

3.1.1 Inclusion Criteria

To be eligible for randomisation into this study, each patient must fulfil the following criteria:

1. Male or female, ≥ 18 years of age at the time of consent.
2. Admitted to hospital due to the severity of their COVID-19¹.
3. Positive virus test for SARS-CoV-2 using a validated molecular assay or validated antigen assay.

Patients who have a positive virus test for SARS-CoV-2 prior to hospitalisation will be randomised no later than 48 hours after hospital admission. If the virus test is performed more than 96 hours prior to hospitalisation, the test will have to be repeated in the hospital prior to randomisation. Only patients whose repeated virus test is positive will be randomised, no later than 48 hours after confirmation of SARS-CoV-2 infection.

¹ Patients admitted to the hospital for reasons that are non-COVID-19 related, who subsequently develop clinical symptoms of COVID-19, test positive for SARS-CoV-2, and require prolongation of their hospital admission, as a consequence of COVID-19, and require treatment with supplemental oxygen (via nasal prongs or mask), must be discussed with the Sponsor's medical monitor prior to randomisation, to assess suitability for the trial.

Patients who have their first positive virus test for SARS-CoV-2 after hospitalisation will be randomised, no later than 48 hours after confirmation of SARS-CoV-2 infection.

4. Require oxygen therapy via nasal prongs or mask (WHO OSCI score of 4).
5. Provided informed consent.
6. Female patients must be ≥ 1 year post-menopausal, surgically sterile, or using a highly effective method of contraception. Acceptable highly effective methods of contraception include:
 - bilateral tubal occlusion
 - intrauterine device (provided coils are copper-banded)
 - levonorgestrel intrauterine system (e.g., CCI [REDACTED])
 - medroxyprogesterone injections (e.g., CCI [REDACTED])
 - etonogestrel implants (e.g., CCI [REDACTED], CCI [REDACTED])
 - normal and low dose combined oral pills
 - norelgestromin/ ethinylestradiol transdermal system
 - intravaginal device (e.g., ethinylestradiol and etonogestrel), desogestrel (e.g., CCI [REDACTED])
 - total sexual abstinence (defined as refraining from heterosexual intercourse)
 - vasectomised sexual partner.

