6.10 Quality of Life Measured Using EQ-5D-5L

The EQ-5D-5L health-related quality of life questionnaire will be completed on Day 0, Day 7, Day 15, Day 28, Day 60 and Day 90 for all patients (see Appendix D).

In addition, the mobility, self-care and usual activities dimensions of the questionnaire will be assessed daily from Day 1 to Day 35.

The EQ-5D-5L provides a simple descriptive profile and a single index value for health status. The EQ-5D-5L self-rated questionnaire includes a visual analogue scale (VAS), which records the respondent's self-rated health status on a graduated (0–100) scale, with higher scores for higher health-related quality of life. It also includes the EQ-5D-5L descriptive system, which comprises 5 dimensions of health: mobility, self-care, usual activities, pain/discomfort, and anxiety/depression. The responses record five levels of severity (no problems/ slight problems/ moderate problems/ severe problems/ extreme problems) within a particular EQ-5D dimension. This questionnaire should only be completed if an approved translation in the language required by the patient is available. If an approved translation is not available, this assessment will not be conducted and will not be recorded as a protocol deviation.

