#### **9.3.3 NEWS2 Score**

The absolute NEWS2 scores and the change from baseline in NEWS2 score will be summarised for hospitalised patients at each scheduled assessment. Generally, NEWS2 score will only be calculated from the data recorded in the NEWS2 CRF. However, baseline NEWS2 score will be calculated from the data entered in the vital signs and level of confusion CRFs for the last assessment prior to first dose. NEWS2 scores will be calculated and summarised from data collected in the NEWS2 CRF for the Pre-dose and Day 1 assessments, however the change from baseline will not be summarised because as per the protocol these assessments could be pre or post dose.

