#### **9.3.4 Quality of Life**

Quality of life as measured by the EQ-5D-5L will be summarised by descriptive statistics of the crosswalk index value, the LSS, the Visual Analogue Scale (VAS) and the usual activities dimension at each scheduled visit.

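### SAP 5.3.4 limits the EQ-5D-5L index to patients at home, so as written there is no Day 0 index and the Day 7, 15 and 28 summaries cover only discharged patients, while SAP 9.3.4 sets no such limit

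*SAP*

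**What the plan says.** The derivation rule is in SAP 5.3.4: "Index values will be calculated for patients in the home setting from their EQ-5D-5L profiles". The section gives no rule for a profile completed in hospital. It later says that "the UK crosswalk index will be used for all patients", but that sentence deals with countries that have no value set of their own. It is about which tariff to apply, not where the patient is.

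Protocol 6.10 says that the full questionnaire "will be completed on Day 0, Day 7, Day 15, Day 28, Day 60 and Day 90 for all patients", provided an approved translation exists. Protocol 5.3.1 to 5.3.4 schedule it for inpatients as well: before the first dose, then on Days 7, 15 and 28 for those still in hospital.

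Protocol 3.1.1 requires that patients be "Admitted to hospital due to the severity of their COVID-19" and "Require oxygen therapy via nasal prongs or mask (WHO OSCI score of 4"). The scale in Protocol 6.6 classes a score of 4 as hospitalised.

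SAP 9.3.4 plans descriptive statistics of the "crosswalk index value, the LSS, the Visual Analogue Scale (VAS) and the usual activities dimension at each scheduled visit". It sets no location limit. The section just before it, SAP 9.3.3, does state one for NEWS2, whose scores "will be summarised for hospitalised patients at each scheduled assessment". SAP 15, which lists departures from the protocol, does not mention the home-setting limit.

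**The concern.** Quality of life by EQ-5D-5L is a named secondary endpoint, and the index is the first of its four planned summaries. Two things follow if a programmer applies SAP 5.3.4 literally.

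First, the index has no baseline. Protocol 8.5 says in general terms that changes from baseline will be evaluated where applicable. For the index this would be impossible, and the arms could not be compared on it before treatment.

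Second, at any visit when some patients are still in hospital, the index table describes only those already discharged. Discharge happens after randomisation and is one of the two primary endpoints. If SNG001 changes the rate of discharge, the two columns of the table hold differently selected patients and are no longer a randomised comparison. The level sum score, built from the same five answers, would sit in the same set of summaries with a different denominator.

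There is also a plain inconsistency. Someone programming from 5.3.4 and someone programming from 9.3.4 would produce different tables.

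**Working it through.** **Inputs.** Placebo discharge of 70% by Day 28, 305 patients per arm, a discharge hazard ratio of 1.45 and 25% dropout over 28 days come from Protocol 8.1. The exponential form and a discharge hazard ratio of 1.7 come from the simulation description in SAP 6. Because the documents give two hazard ratios for discharge, both are carried through. I take discharged to mean in the home setting.

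**Reproducing the plan's figures.** The placebo rate is λ = ln(100/30)/28 = 0.0430 per day. The median is ln 2/λ = 16.12 days, against 16.1 in the SAP. With a hazard ratio of 1.7 it is 16.12/1.7 = 9.48 days, against 9.5 in the SAP. The share discharged by Day 28 on placebo is 1 − exp(−28λ) = 70.0%.

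**Share with an index under SAP 5.3.4.** For day t and hazard ratio h this is 1 − exp(−λht), which equals 1 − 0.3^(ht/28). Death, readmission and dropout are ignored. Counts are out of 305. Day 0 is zero because all eligible patients are inpatients.

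| Day | Placebo | SNG001, HR 1.45 | SNG001, HR 1.7 | Gap, points |
|---|---|---|---|---|
| 0 | 0% (0) | 0% (0) | 0% (0) | 0 |
| 7 | 26.0% (79) | 35.4% (108) | 40.1% (122) | 9 to 14 |
| 15 | 47.5% (145) | 60.8% (185) | 66.6% (203) | 13 to 19 |
| 28 | 70.0% (214) | 82.5% (252) | 87.1% (266) | 13 to 17 |

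So about 60% to 74% of patients would have no index at Day 7. These are shares discharged, not estimates of bias. The plan gives no discharge rate after Day 28, so I compute nothing for Days 60 and 90.

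**Allowing for dropout.** If the 25% dropout is independent of discharge, the Day 28 shares become 0.75 × 70.0% = 52.5% on placebo, and 0.75 × 82.5% = 62% (HR 1.45) or 0.75 × 87.1% = 65% (HR 1.7) on SNG001. The levels fall and the gap between arms remains.

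**What selection alone could do.** This step uses assumptions that are not in the documents. Suppose the drug has no effect on quality of life and moves every patient's discharge forward by the hazard ratio. Suppose also that quality of life correlates r with a normal score that ranks patients by how early they leave. The discharged group is then the top share p of that score, with mean quality of life r·φ(z)/p in SD units, where z cuts off the upper share p. At Day 15, φ(z)/p is 0.838 on placebo, 0.633 at HR 1.45 and 0.546 at HR 1.7. The spurious difference is then 0.3 × (0.633 − 0.838) = −0.06 SD at the mild end and 0.6 × (0.546 − 0.838) = −0.18 SD at the strong end. Over Days 7 to 28, with r from 0.3 to 0.6, the range is about −0.06 to −0.18 SD. The sign comes from the assumptions.

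**The case against.** The strongest reply is that SAP 5.3.4 never says the index is derived solely at home. SAP 9.3.4 has no location limit, while the SAP does write one into the analysis section for NEWS2. The phrase may therefore be unintended residue. SAP 8.5 makes a similar hospital and home split for medications, and Table 23 still refers to each SNG001 arm in a two-arm trial. That is plausible, but the documents do not establish it. It supports reconciling the two sections rather than leaving them alone, because 5.3.4 is the only derivation rule and says nothing about in-hospital profiles.

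The second reply concerns weight, and it stands. SAP 9.3.4 plans no test, no model and no change from baseline for EQ-5D-5L. The measure has no estimand in Table 23 and no place in the multiple testing scheme. The level sum score uses the same five items, has no home limit and is available from Day 0. So are the visual analogue scale and the usual activities dimension.

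A reader might infer more: that faster discharge on SNG001 would bring sicker patients into its summary and make a real benefit look like no difference or harm. The documents do not support that. They give no relation between quality of life and time of discharge. If the drug speeds discharge by making patients better, the additional discharged patients need not be worse off. The −0.06 to −0.18 SD above shows what one set of assumptions would produce. It is not a finding about this trial.

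Nor should a reader infer that the trial's quality-of-life results as a whole rest on discharged patients. That applies to one of the four EQ-5D-5L summaries.

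**Conclusion.** The point holds as a minor one. Applied literally, SAP 5.3.4 leaves the index undefined at Day 0 and makes its by-arm summaries at Days 7, 15 and 28 conditional on discharge. It also disagrees with SAP 9.3.4, and no reason for the limit is given. Neither the missing baseline nor the conditioning needs any numerical assumption. They follow from the derivation rule, the eligibility criteria and the assessment schedule.

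The illustrative imbalance in who contributes is 9 to 19 percentage points between arms. It rests on the plan's exponential model and on discharge hazard ratios of 1.45 to 1.7. It would vanish if the drug did not change discharge. Neither the primary nor the key secondary analyses are touched.

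**What to change.** Delete the four-word home-setting qualifier from the first sentence of SAP 5.3.4, so that the index is derived for every complete EQ-5D-5L profile, in hospital or at home, including Day 0. That brings 5.3.4 into line with 9.3.4. Show the number contributing per arm at each visit; SAP 8 already includes the number of subjects in continuous summaries.

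If the limit was deliberate, give the reason, repeat it in 9.3.4, and label the index table as conditional on discharge.

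The cost is four words and no new data collection, since the protocol already schedules the in-hospital questionnaires. If the change comes after unblinding for the primary analysis, SAP 7.4.5 requires it to be documented in the clinical study report. The revised summary will still depend on patients being alive and able to answer, so it should not be described as free of selection.
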